WMO	Medical Research Involving Human Subjects Act; in Dutch: Wet Medisch-wetenschappelijk Onderzoek met Mensen

SUMMARY

Rationale: Hepatocellular adenoma (HCA) is an uncommon, solid and benign liver lesion. Typically, it is a solitary lesion found in women within their reproductive years and it is strongly associated with the use of oral contraceptive medication (OC). Development of HCA is also associated with obesity and metabolic syndrome. More recently, studies have shown a rising incidence of HCA diagnosis, current prevalence is estimated to be between 0.001 and 0.004%. HCA consists of several subtypes: inflammatory, steatotic, β -catenin mutation associated and unspecified. A higher BMI is associated with inflammatory HCA, which is also associated with multiple lesions. Steatotic HCA more often consist of single lesions.

Management of HCA requires a multidisciplinary approach. For female patients, it depends on the associated symptoms, lesion size and location. All female patients are advised to stop using OC and maintain a healthy body weight. Women with HCA can be included in a surveillance period ("Wait-and-see"-strategy) for 6 months, after which a contrast-enhanced magnetic resonance imaging (MRI) is performed. The aim is to predict if larger lesions (>5cm) will regress, thus avoiding unnecessary surgery. Treatment modalities to further enhance the regression and avoid surgery are an interesting research possibility. As overweight is frequently observed in women with liver adenoma, metabolic changes are assumed to play a role and diet may help to reduce tumour size.

Dietary restriction, defined as reduced intake of food without malnutrition, may be effective. It's associated with metabolic changes, extended life span, lower risk of age associated diseases, improved fitness and increased resistance to acute stress. In combination with a ketogenic diet, it also reduces portal insulin concentrations, which down-regulate hepatic growth hormone receptors and reduces IGF-I synthesis. A recent study also shows the beneficial effect of eucaloric very-low-carbohydrate diet on disease control of acromegaly patients. Dietary restriction can be performed in different regimens such as short-term fasting or up to 30% reduced daily calorie intake. To explore the potential efficacy of dietary restriction, we aim to investigate whether the beneficial effects of a ketogenic diet with slight caloric restriction might increase the regression of HCA. This will further strengthen the treatment modality of close observation and avoid surgical resection.

Objective: to determine the effect of dietary restriction and the ketogenic diet on the regression of hepatocellular adenoma after 6 months.

Study design: A single-centre matched cohort study

Study population: Female subjects with a hepatocellular adenoma, who are entering a surveillance period including cessation of oral contraceptive medication and regular dietary advice.

Intervention: a ketogenic diet with +/- 30% less calories (approximately 35gr carbohydrate/ 1500 kcal per day) for 3 months, followed by a less strict ketogenic diet for 3 months (approximately 60gr carbohydrate/ 1500 kcal per day)

Main study parameters/endpoints: The difference in regression of the liver adenoma after 6 months compared to historical controls and the feasibility / adherence of the dietary intervention. Other secondary endpoints are Quality of Life, change in body weight, body composition, resting energy expenditure and plasma parameters.

Nature and extent of the burden and risks associated with participation, benefit and group relatedness: The extent of the burden of our study is considered low. Dietary restriction and the ketogenic diet have been proven feasible and safe in previous studies. For this study, three extra blood samples by 3 venous punctures are taken. No extra visits to the hospital or imaging studies are needed in order to obtain all the information required for this study. Several standardized questionnaires are asked to be filled in during and after the diet. Mentioned questionnaires take about 10 minutes to complete. No other risks concerning the dietary intervention are to be expected.

1. INTRODUCTION AND RATIONALE

Hepatocellular adenoma (HCA), also known as hepatic adenoma, is an uncommon, solid, benign liver lesion (1-5). Typically, it is a solitary lesion found in young women within their reproductive years. HCA has been widely associated with the use of oestrogen-containing medication, f.i. contraceptive pills. The annual incidence of HCA in users of OCs has been estimated to be 30-40 cases per million OC users in comparison with one case per million non-users (1, 2). In several studies a consistent effect of sex-hormones in the development of HCA has been found. A 30-40 fold increase in the incidence has been confirmed in long term users of contraceptive pills (1, 6, 7). A dose-related risk ratio and regression after cancellation of use of contraceptive pills further confirmed the effect of sex-hormones in the development of HCA (4, 5, 8, 9). More recently, studies show a rising incidence of HCA diagnosis (10), current prevalence is estimated to be between 0.001 and 0.004% with an reported female: male ratio of 10:1 (11, 12). In large part this increasing incidence may be attributed to an increased discovery of incidental/asymptomatic HCA by extensive use of imaging.

HCA development is also associated with obesity, metabolic syndrome (10, 13-15) anabolic androgen use (16-18), rare genetic syndromes including glycogen storage diseases and familial adenomatous polyposis (3, 19, 20), especially in men (10, 13, 14). The mechanism causing the increased risk of developing HCA in metabolic syndrome has not been completely identified (13). HCA consists off several subtypes: inflammatory, steatotic, β -catenin mutation associated and unspecified (13, 15, 21). A higher BMI is associated with inflammatory HCA, which is also associated with multiple lesions (15). Steatotic HCA more often consist of single lesions (15).

A hepatocellular adenoma typically is detected by various ways. First, as an incidental finding on routine imaging on asymptomatic individuals. Secondly, as a symptomatic lesion presenting by pain in the right upper quadrant. Less often, the lesion may be detected because of acute haemorrhage resulting from rupture. This can be a life-threatening event if not identified on time (11, 21-24) and if the HCA ruptures into the abdominal cavity (3, 24). The risk of bleeding is increased if the HCA is larger than 5cm, use of hormones, pregnancy, exophytic morphology and an inflammatory subtype (24-26). A recent systematic review showed that the frequency of haemorrhage is 27,2% and a rupture with intraperitoneal bleeding was reported in 17,5% of patients (22, 24).

HCA is diagnosed by typical findings on ultrasound imaging and contrast-enhanced, cross-sectional imaging by MRI (22, 23, 27). For female patients a biopsy or fine-needle aspiration is not indicated (22, 23, 27). For male patients the diagnosis needs to be confirmed pathologically to exclude a malignant lesion (22, 23, 27).

Management of HCA requires a multidisciplinary approach. Men who are diagnosed with HCA are advised to undergo surgical resection. The rate of malignant transformation is significantly higher in males (47%) compared to females (4%) (11, 28). For female patients,

the management depends mainly on the associated symptoms, lesion size and location. All female patients are advised to stop using contraceptive medication and strive for a healthy body weight (4, 9, 22, 29, 30). Women with (a)symptomatic HCA can be subjected to a surveillance period for 6 months, after which a contrast-enhanced MRI is performed to check regression of the HCA. If the follow-up MRI shows a rapid regression or a lesion smaller than 5cm, further follow-up will be conducted (22, 23). Other treatment strategies are based on an internally validated model to predict regression (30). If the adenoma increases in size or shows heterogenous parts, surgical resection will be planned (22, 23). For a flowchart helpful in making decisions concerning the management of HCA, see figure 1.

[figure not shown]

Figure 1: Flowchart helpful in deciding a management strategy for HCA, from van Aalten et al.

Management of hepatocellular adenoma in pregnant women or women with an active wish to conceive should require extra consideration. There may be an added risk of hormone-induced growth and therefore spontaneous haemorrhage (31-33). Currently, negative advice for pregnancy is only justified in women having tumours larger than 5 cm or those who have experienced complications of HCA in earlier pregnancies. In these cases, surgical resection before pregnancy should be considered (31-33). When a known asymptomatic HCA of <5cm is present, there is no evidence to advise against pregnancy (32, 33). For growing lesions or symptomatic lesions, treatment by surgical resection or trans-arterial embolization (TAE) is advocated before pregnancy.

Currently, treatment of (a)symptomatic HCA's focuses on a wait-and-see / active surveillance policy, aiming to reduce surgery. It consist of a 6-months observation period after which a MRI is performed (22, 23, 34). A model will be used to calculate a projected chance of regression in 1 or 2 years (30). Further treatment will be based on patient characteristics, size and regression of the HCA, projected chance of complete regression

and imaging characteristics of the HCA. Treatment modalities to further enhance regression are subject for research. Faster regression of the HCA could reduce patient's anxiety, waiting time, lead to a more reliable prediction of regression at one year and finally less surgical interventions.

Dietary / Caloric restriction (DR), meaning reduced intake of food without malnutrition, is associated with extended life span, lower risk of age associated diseases, improved fitness and increased resistance to acute stress (35-40). Caloric restriction can be performed in different regimens such as short-term fasting, or up to 30% reduced daily calorie intake for several weeks, or even indefinitely. Dietary restriction represents a non-invasive, non-expensive method of acquiring long term health benefits (40, 41). In combination with a ketogenic diet, it also reduces portal insulin concentrations, which down-regulate hepatic growth hormone receptors (42) and reduce IGF-I synthesis (43, 44). Caloric restriction and ketogenic diet also share biological responses implicated in metabolite-controlled longevity pathways, via production of ketone bodies. Production of ketone bodies such as β -hydroxybutyrate from fatty-acid catabolism may operate as endogenous histone deacetylase (HDAC) inhibitors and may contribute to epigenetic control of gene expression, DNA repair, and genome stability (45). Ketogenesis also promotes synaptic plasticity and neurogenesis by increasing the expression of brain-derived neurotrophic factor (BDNF) (45). Dietary restriction and/or fasting further increases expression of cytoprotective genes, increases immunomodulation via increased anti-inflammatory cytokine production and also decreases the expression of inflammatory markers (46-48). So far, the benefits of fasting and/or dietary restriction in rodents (46, 47, 49-51) have partly been translated to humans. DR has been proven feasible and safe in well-nourished patients who are opting for surgery (52-54).

The classic ketogenic diet is a high-fat, adequate-protein, low-carbohydrate diet that produces metabolic changes associated with the starvation state (55-58). Changes in plasma ketones, insulin, glucose, glucagon, and free fatty acids can occur within hours of starting the diet and can be profound (55). A recent study also shows the beneficial effect of eucaloric very-low-carbohydrate ketogenic diet on disease control of acromegaly patients via lowering of IGF-1 levels (59). In a recent randomized controlled trial, patients with type 2 diabetes improved their glycaemic control and lost more weight after being randomized to a very low-carbohydrate ketogenic diet and lifestyle online program rather than a conventional, low-fat diabetes diet online program (57). Potential side effects of the ketogenic diet include constipation, diarrhoea, nausea, vomiting, and very rarely pancreatitis (60-62). The side effects can lessen with continued diet use and minor adjustments under supervision of a dietician. Pharmaceutical intervention or diet discontinuation is rarely indicated.

To further strengthen the “the wait-and-see / active surveillance” strategy as a successful treatment modality of HCA we aim to investigate whether the beneficial effects of a ketogenic diet with moderate caloric restriction might increase the rate of regression of HCA.

2. OBJECTIVES

Primary Objective: to determine the effect of a moderate calorie restricted, ketogenic diet on the reduction in size of hepatocellular adenoma after 6 months in adult female patients.

Secondary Objectives:

- To determine the feasibility / adherence to the ketogenic diet
- To identify predictors of the primary endpoint
- To assess possible change in the estimated chance of HCA regression to 0,5 cm at 1-2 years due to the ketogenic diet, estimated by prediction model.
- To determine the change in liver fat content
- To investigate potential side effects & burden of diet
- To determine the effect on Quality of Life (QoL)
- To assess change in body weight and plasma parameters
- To investigate the effect of the diet on change in body composition and resting energy expenditure

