10.1 Primary study parameter

The primary endpoint is the reduction in size (in cm) of the largest diameter of the largest hepatocellular adenoma after 6 months, compared to our matched historical controls. A multivariable linear regression model will be used to estimate the difference in tumour regression between the treatment group and the historical control group. The model will be adjusted for age, change in body weight, the ketogenic diet and oral contraceptive use at baseline.

Subpopulation: the same model will be constructed but will not be adjusted for oral contraceptive use at baseline.

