10.2 Secondary study parameters

In the secondary analysis, the multivariable linear regression model analysis from the primary analysis will be used to identify independent variables (age, change in body weight, subjected to ketogenic diet and oral contraceptive use at baseline) as predictors of the primary endpoint. An additional analysis will be performed including adherence to the diet as independent variable.

Analysis for adherence to the ketogenic diet will be done via descriptive statistics. Adherence to the diet will be calculated as a percentage.

Side effects of the ketogenic diet will be analyzed via descriptive statistics. Occurrence of side effects will be given as a percentage.

Results of the prediction model/chance assessment tool (30), providing the estimated chance (%) of HCA regression to 0,5 cm at 1 and 2 years after diagnosis will be compared between our intervention group and the matched historical controls by the Chi-square test.

Change in liver fat content (%) will be compared in our intervention group by a multivariable linear regression model. The independent variables in this model will include age, change in body weight and oral contraceptive use at baseline. An additional analysis will be performed including adherence to the diet as independent variable.

Changes in plasma parameters will be compared in our intervention group by using descriptive statistics, t-test in the case of continuous outcome variables with normal distribution or non-parametric test in the case of non-normality. The Chi-square test will be used for categorical data.

Change in quality of life will be compared over time in our intervention group by a mixed-effects model analysis, taking repeated measurements into account. The independent variables in this model will include age and change in body weight. An additional analysis will be performed including adherence to the diet as independent variable.

Mean change in body weight, change in body composition and resting energy expenditure will be estimated in our intervention group by a mixed-effects model analysis, taking repeated measurements into account. The independent variables in this model will include age and sex. An additional analysis will be performed including adherence to the diet as independent variable.

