11.4 Benefits and risks assessment, group relatedness

Based on the hypothesis and earlier studies that long-term caloric restriction and the ketogenic diet induce beneficial effects, the diet intervention group may experience better subjective wellbeing and weight loss compared to those in the control group. Potential side-effects can be managed by the dietician involved. This study aims to investigate the merits of caloric restriction and the ketogenic diet in the treatment of hepatocellular adenoma.

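### Quality of life and body composition/resting energy expenditure are stated as effects of the diet, and 11.4 expects a gain over controls in wellbeing and weight, but the plan analyses only uncontrolled change in the diet arm

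*Protocol*

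**What the plan says.** Section 2 lists two secondary objectives in causal terms: "To determine the effect on Quality of Life (QoL" and "To investigate the effect of the diet on change in body composition and resting energy expenditure". A third is purely descriptive: "To assess change in body weight and plasma parameters". Section 11.4 adds a comparative expectation, that "the diet intervention group may experience better subjective wellbeing and weight loss compared to those in the control group".

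Section 8.2 allocates every subject to the diet, so the only comparator is the matched historical cohort of section 3. The plan uses that cohort for tumour regression (10.1), the prediction-tool result (10.2) and baseline characteristics (10.3). The outcomes at issue here are analysed without it: "Change in quality of life will be compared over time in our intervention group", and "Mean change in body weight, change in body composition and resting energy expenditure will be estimated in our intervention group by a mixed-effects model analysis". Section 10.3 again models resting energy expenditure in the intervention group alone.

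The Summary describes care that applies to everyone: "All female patients are advised to stop using OC and maintain a healthy body weight". It also defines the study population as women entering a surveillance period that includes stopping oral contraceptives (OC) and regular dietary advice.

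**The concern.** An effect of the diet means a difference from what would have happened without it. In the main population, life without the diet is not a static baseline. It is a surveillance period with weight advice and OC cessation, both of which can move quality of life, body composition and energy expenditure. The protocol itself expects this to some degree: in section 8.3 the clinician consultation covers complaints after OC are stopped.

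Before-after change in the diet arm therefore mixes the diet with standard care. If the report follows section 2, the whole change may be presented as the effect of the diet. If it follows 11.4, it would need a comparison with controls that no planned analysis provides for wellbeing or weight.

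**Working it through.** **Step 1. Objective against analysis.**

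| Outcome | Wording in section 2 | Planned analysis | Controls used | Do they match? |
|---|---|---|---|---|
| Tumour size | effect | 10.1, regression with historical controls | yes | yes |
| Quality of life | effect | 10.2, mixed model in diet arm; age, weight change | no | no |
| Body composition, resting energy expenditure | effect | 10.2, mixed model in diet arm; age, sex (energy expenditure again in 10.3, with compliance added) | no | no |
| Body weight | change | 10.2, mixed model in diet arm; age, sex | no | yes for section 2, no for 11.4 |
| Plasma parameters | change | 10.2, tests in diet arm | no | yes |

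The mismatch covers two objectives, plus the wellbeing and weight sentence in 11.4.

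**Step 2. What one arm can identify.** Write the mean change in the diet arm as D + S, where D is the part due to the diet and S the part that standard care would have produced anyway. One arm gives one number for two unknowns. With matched controls whose mean change is S, the difference (D + S) − S = D. The models in 10.2 and 10.3 do not supply S. Age does not, and sex is constant in an all-female study. Adherence, in the additional analyses, is self-selected, so a gradient with adherence is not a controlled effect.

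**Step 3. Is a control available?** For body weight the plan implies that one is. Of the primary model, which contains both groups, section 10.1 says "The model will be adjusted for age, change in body weight, the ketogenic diet and oral contraceptive use at baseline". Every control in that model needs a value for weight change, yet section 3 mentions weight for the controls only as a baseline matching variable. Either follow-up weights exist, and a controlled weight comparison needs no new data, or they do not, and the 10.1 model cannot be fitted as written. For quality of life, body composition and energy expenditure, nothing in the protocol indicates that control data exist.

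**Step 4. Size.** The plan gives no figure for S, so this step is an illustration on assumed values. Take D = 0, and let S be b standard deviations of the change score. Use a two-sided paired t-test at 0.05 as a simple stand-in for the mixed model. The arm size is 51, the requirement in section 4.4, which was calculated for tumour diameter and not for these outcomes. The test statistic has noncentrality b × √51, with √51 = 7.14.

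| Assumed b | Noncentrality | Chance of a significant before-after change |
|---|---|---|
| 0 | 0 | 5% |
| 0.1 | 0.71 | 11% |
| 0.2 | 1.43 | 29% |
| 0.3 | 2.14 | 56% |
| 0.5 | 3.57 | 94% |

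These results would be correct as statements about change. They would be wrong only if read as effects of the diet.

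**The case against.** The best defence is that this is a proof-of-concept study whose controlled comparison is reserved for tumour outcomes. Sections 10.2 and 10.3 say openly that the other analyses are confined to the intervention group, and 11.4 is a benefit-risk expectation, not an endpoint. Much of this stands. The analyses are legitimate as descriptions, and for questionnaire, impedance and calorimetry outcomes the limitation comes with a single-arm design. It does not remove the mismatch, because section 2 still promises effects that these analyses cannot deliver.

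A reader might infer more than the documents support:

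- *That the weight and plasma objective is also mis-stated.* It asks only for change, and the analysis answers that. Some plasma markers, such as β-hydroxybutyrate, are in any case tied directly to ketosis.
- *That OC cessation and diet start on the same day and can never be separated.* The protocol places both in the surveillance period but does not fix OC cessation at baseline. Recruitment is at the second clinic visit with a week for reflection (11.2), so some women may have stopped earlier.
- *That the bias favours the diet, or has a known size.* No control change is reported. Complaints after stopping OC could push quality of life the other way.
- *That adding baseline OC use as a covariate repairs the models.* In a repeated-measures model a main effect shifts the level, not the change over time.
- *That the subpopulation is a clean check.* Its OC advice preceded entry, but it is a pilot of 20 women selected for little or no regression, and section 3 separates its analysis because it expects confounding.

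**Conclusion.** The point holds for the quality-of-life objective, the body-composition and resting-energy-expenditure objective, and the comparative sentence in 11.4, which is also where the mismatch for weight lies. In the main population the planned analyses estimate change during diet plus standard care, and cannot attribute it to the diet. Neither the size nor the direction of the resulting error can be determined from the documents. The 11% to 56% range for a background change of 0.1 to 0.3 standard deviations rests on an assumed shift, a true diet effect of zero, 51 women and a paired t-test. It shows only that a modest background change is enough to matter.

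These are secondary outcomes of a proof-of-concept study, and the primary tumour comparison, which has a control group, is not affected by this point. The correction is still worth making before analysis, because it decides what the report may claim.

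**What to change.** 1. In 10.2, add a comparison of six-month change in body weight between the diet group and the matched historical controls, using the control weight change that the 10.1 model already requires. State how close to six months the control weights must lie. If those data do not exist, say so and correct 10.1 as well. The comparison remains non-randomised and should be described that way.
2. In section 2, reword the quality-of-life and the body-composition/resting-energy-expenditure objectives as change from baseline during the diet plus standard care. Reword the comparative sentence in 11.4 in the same way. Leave the weight and plasma objective as it is.
3. Optionally, report these changes by baseline OC use, through an OC-by-time term and not only a main effect, labelled as descriptive.

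The cost is protocol wording, one added comparison and at most one extra model term, with no new visits or measurements for participants. If control weights have to be retrieved, that work is already implied by 10.1. The downside is a more modest claim for these secondary outcomes.
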